11.11. Summary – Study Flow and Study Evaluations

The flow of subject participation, visits and evaluations is depicted as a schematic in **Figure 11**.

*Otoscopic examination, tympanometry and audiometry are considered standard of care for this patient population. Data obtained from these assessments within 4 weeks prior to study informed consent may be included as screening assessments.

† If tube(s) have been confirmed to have extruded, no additional follow-up visits are required and the subject may exit prior to the 24 month visit.

Figure 11. Schematic of Study Design Flow

The schedule of evaluations for each study visit is presented in **Table 4**.

Table 4. Table of Evaluations

Evaluation	Screening	Procedure	3 Weeks (-/+ 7 days)	6, 12, 18, 24 months [†] (-/+ 28 days)
Informed Consent	✓			
Medical History	✓			
Cranial Nerve Physical Exam*	✓	✓	✓	
Concomitant Medications	✓	✓	✓	✓
Inclusion/ Exclusion Criteria	✓	✓		
Otoscopy	✓ (**within 28 days prior to Procedure)	✓	✓	✓
Tympanometry	✓ (**within 28 days prior to Procedure)		✓	✓
Audiometry	✓ (**within 28 days prior to Procedure)		✓	
Procedure		✓		
Anesthesia Effectiveness*		✓		
Tube Placement Tolerability*		✓		
Suction Tolerability*		✓		
Post-Procedure Tolerability		✓		
Adverse Events		✓	✓	✓
Study Exit				✓

*Anesthesia effectiveness, cranial nerve physical exam and tolerability assessments for in-office subjects only.

** Otoscopic examination, tympanometry and audiometry are considered standard of care for this patient population. Data obtained from these assessments within 28 days prior to procedure may be included as screening assessments.

† If tube(s) have been confirmed to have extruded, no additional follow-up visits are required and the subject may exit prior to the 24 month visit.

12.0 ASSESSMENT OF SAFETY

12.1. Adverse Events

All reported or observed adverse events that occur during or after the procedure will be recorded. The study Investigator will determine whether an adverse event has occurred, whether life-threatening, serious or non-serious. Pre-existing conditions should not be reported as adverse events unless there has been a worsening in the severity or frequency, which cannot be attributed to natural history or progression of the disease. This definition does not depend on the causal relationship with the device, drug or protocol requirements.

Any change of clinical significance, including vertigo, nausea and vomiting, derived from the protocol evaluations including observations and patient-reported findings will be included as adverse events. Adverse events will also include operative and recovery observation for lead-in procedures conducted in the OR with general anesthesia including, but not limited to, clinically-meaningful vital sign changes, emergence delirium, post-operative nausea, vomiting, disorientation, and complications related to intubation or induction.

All Adverse Events (AEs) will be recorded on dedicated AE case report forms. The event, date of onset, severity, seriousness, duration, treatment, outcome, date or resolution and relationship to device, procedure or drug will be recorded on the AE case report form (CRF). AEs will be categorized by seriousness, relatedness to procedure, investigational drug, or device whether anticipated or unanticipated. All adverse events will be coded using standard terms.

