10.6. Safety Endpoint

Safety: The occurrence of all adverse events, by subject. The totality of the safety data will be summarized and presented. Safety events will be reported for all in-office subjects in which the lidocaine solution was introduced into the ear, or introduction of TDS in ear for OR lead-in subjects) (see **Section 13.2.3**), [REDACTED]

[REDACTED]
[REDACTED]
[REDACTED]

Safety data will be presented separately as follows:

- Lead-In OR Cohort
- Lead-In Office Cohort*
- Pivotal Cohort*

[REDACTED]
[REDACTED]

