- *Unilateral or bilateral* TT insertion for recurrent acute otitis media (AOM) with unilateral or bilateral middle ear effusion at the time of assessment for tube candidacy, where recurrent AOM is defined as three or more AOM episodes in the past 6 months or at least 4 AOM episodes in the past 12 months with at least 1 in the past 6 months.
- *Unilateral or bilateral* TT insertion in at-risk children with unilateral or bilateral OME, *respectively*, that is unlikely to resolve quickly as reflected by a type B (flat) tympanogram or persistence of effusion for 3 months or longer (chronic OME). At risk children have increased risk for speech, language or learning problems from otitis media because of baseline sensory physical, cognitive or behavioral factors.

In this study, the caregiver will be informed of the risk of subsequent OME or AOM in the contralateral ear and the potential need for a second tube insertion procedure should this occur. Prior to procedure, the Investigator must document which ears are intended for in-office tube placement.

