12.3. Adverse Event Definitions

Adverse Event (AE)

An AE is any unfavorable and unintended sign, symptom, or disease temporally associated with the procedure or use of the device or investigational drug, and does not imply judgment about causality.

Serious Adverse Event (SAE)

AEs are classified as serious or non-serious. A serious adverse event is any AE that is:

- Fatal
- Life-threatening
- Requires or prolongs hospital stay

- Results in persistent or significant incapacity or substantial disruption of the ability to conduct normal life functions
- Led to fetal distress, fetal death or congenital abnormality or birth defect
- An important medical event that may jeopardize the subject, and may require medical or surgical intervention to prevent one of the other serious outcomes noted above.

Life Threatening Adverse Event or Life-Threatening Suspected Adverse Reaction

An adverse event or suspected adverse reaction is considered life threatening if, in the view of either the investigator or sponsor, its occurrence places the subject at immediate risk of death. It does not include an adverse event that, had it occurred in a more severe form, might have caused death.

Unanticipated Adverse Device Effect (UADE)

A UADE is any serious adverse effect on health or safety or any life-threatening problem or death caused by, or associated with, a device, if that effect, problem or death was not previously identified in nature, severity, or degree of incidence in the investigational plan or application, or any other unanticipated serious problem associated with a device that relates to the rights, safety, or welfare of subjects.

In order to ensure subject safety during the study, all adverse events assessed as “serious” in the opinion of the Investigator will be reviewed by the Medical Monitor to determine any causal relationship to the study drug, device or procedure. All adverse events that do not meet any of the criteria for serious should be regarded as non-serious adverse events. Non-serious adverse events must still be documented on the appropriate CRF.

Reporting

The sponsor will notify FDA, all reviewing IRBs and all participating Investigators of potential serious risks, from this study or any other source, as soon as possible, but in no case later than 15 calendar days after the Sponsor determines that the information qualifies for reporting, including:

1. Suspected adverse drug reactions that are considered both serious and unexpected,

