Possible	A clinical event, including laboratory test abnormality, with a reasonable time sequence to procedure, device or drug administration/exposure, but which could also be explained by concurrent disease, other interventions or drugs.
Not Related	A clinical event, including laboratory test abnormality, with a temporal relationship to procedure, device or drug administration/exposure which makes a causal relationship improbable, and in which concurrent disease, other interventions, other drugs or chemicals provide plausible explanations. A Not Related event may also not have a reasonable temporal relationship to procedure, device or drug administration/exposure.

*Causality definitions derived from WHO-UMC Causality Assessment Scale⁶⁸

Adverse Event Criteria – Hearing Loss

Audiometry will be used to assess changes to hearing thresholds for all ears. Investigators will diagnose post-treatment hearing impairment/loss if audiometry indicates a greater than 15-decibel (dB) change (worsening) in air conduction pure tone average for either ear. Classification of the level of hearing loss/impairment will be according to the American Academy of Audiology Childhood Screening Guidelines, as outlined in **Table 8**.^{69,70}

Table 8. Table of Hearing Threshold Change (Worsening) Classification

Level	Threshold Change
Slight	16-25 dB
Mild	26-40 dB
Moderate	41-55 dB
Moderately Severe	56-70 dB
Severe	71-90 dB
Profound	91 dB or greater

[figure not shown]

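### Protocol 12.1 keeps worsening ear disease out of the AE record when it is attributed to natural history; this conflicts with the definition in 12.3 and invites inconsistent recording

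*Protocol*

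**What the plan says.** Protocol 12.1 sets a default: "Pre-existing conditions should not be reported as adverse events". The exception applies "unless there has been a worsening in the severity or frequency, which cannot be attributed to natural history or progression of the disease". The sentence after it adds: "This definition does not depend on the causal relationship with the device, drug or protocol requirements". The following paragraph of 12.1 takes in, as AEs, all clinically significant changes found at protocol evaluations or reported by patients.

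Protocol 12.3 defines an AE as an untoward finding or illness that is "temporally associated with the procedure or use of the device or investigational drug, and does not imply judgment about causality".

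Protocol 12.4 then has the investigator assign causality to every recorded AE using Table 7. Its Not Related category covers events "in which concurrent disease, other interventions, other drugs or chemicals provide plausible explanations". Table 5 in the same section provides severity grades for middle ear inflammation, including serous otitis.

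The safety endpoint in Protocol 10.6 is "The occurrence of all adverse events, by subject". SAP 14.1 tabulates recorded AEs by subject, severity and relationship to device, procedure and drug.

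**The concern.** All the indications in Protocol 11.4.1 are forms of OME or recurrent AOM, the latter defined by, for example, "three or more AOM episodes in the past 6 months". For every treated child the pre-existing condition is therefore disease of the ear that receives the tube. Further infection or returning effusion in that ear is of direct interest for the safety of a tube. It is also what an investigator can most easily describe as the enrolling disease taking its course.

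The clause in 12.1 places that judgement before recording. An event screened out there receives no Table 7 category and is not among the AEs that the Medical Monitor reviews under 12.5. It also does not enter the SAP 14.1 tables. The trial is single-arm and its investigators know the treatment, so no comparison group would share the under-recording or expose it.

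**Working it through.** The documents state no expected AE rate, safety performance goal or safety sample size, so there is no plan figure to reproduce. The check is a comparison of the texts.

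1. **12.1 read literally.** A pre-existing condition becomes reportable only if it has worsened in severity or frequency and that worsening cannot be put down to the disease. Worsening that is put down to the disease fails the second condition and is not an AE.

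2. **12.1 against 12.3.** Under 12.3, a worsening that follows the procedure in time qualifies whatever its cause. Under 12.1 it qualifies only after a judgement about cause. One worsened ear can be an AE under 12.3 and not under 12.1.

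3. **12.1 against the causality step in 12.4.** Not Related exists so that events explained by concurrent disease are recorded and then classified. The 12.1 clause removes some of the events that this category is meant to hold.

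4. **12.1 against its own next paragraph and Table 5.** The paragraph on clinically significant changes, and the grading of serous otitis, both presuppose that middle-ear disease can be an AE. Neither says which instruction prevails. Two sites could follow the protocol in good faith and record the same event differently.

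5. **Direction.** The clause can take events out of the AE record but cannot add any. Let *s* be the share of subjects with a post-procedure ear event whose events are all screened out by attribution. Then

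   reported proportion = (1 − *s*) × true proportion.

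   With *s* = 0 nothing is lost, and any *s* above 0 lowers the reported rate. The documents give neither *s* nor the true proportion, so *s* may lie anywhere from 0 to 1 and no size follows.

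6. **What other data would show.**
   - Tube patency at 3 weeks is a tested secondary endpoint, and patency is examined again at 6, 12, 18 and 24 months until extrusion (Protocol 11.10).
   - SAP 14.4 tabulates tympanogram type by visit.
   - SAP 14.5 tabulates canal and tympanic membrane abnormalities by visit. Effusion is assessed at otoscopy (Protocol 11.4.4), but the visible text of SAP 14.5 does not name it.
   - Concomitant medications are recorded through study exit (Protocol 11.4.2), so treated episodes leave a trace.

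   After week 3 the scheduled visits are six months apart, so an untreated episode that resolves between visits may leave no record. Reconstruction is possible but partial.

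**The case against.** The strongest reply is that the protocol, read as a whole, expects these events to be recorded. The paragraph on clinically significant changes is broad, Table 5 grades middle-ear disease, and visit findings are tabulated separately from AEs. This stands in part: it rules out a claim of certain or systematic omission. It does not settle which instruction governs, and that leaves room for inconsistent recording.

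A second reply is that 12.1 does not flatly contradict itself. Its disclaimer concerns causal relationship with the device, drug or protocol requirements, and natural history is literally a different question. That is fair. In practice, deciding that worsening is due to the disease largely decides that it is not due to the tube, but within 12.1 this is ambiguity. The clear conflict is with 12.3.

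Third, not every ear event falls under the exclusion. A blocked tube cannot pre-exist the procedure. Perforation and otitis externa are exclusion criteria, so drainage through a tube is arguably a new sign. It is lost only if the investigator treats it as an episode of the enrolling disease. Recurrent AOM and returning effusion are the firmer examples.

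Fourth, text is blacked out in Protocol 10.6, 12.4 and 12.5 and in SAP 14.1, and further recording rules may stand there. They could guide sites, but they would not remove the conflict between the visible sentences.

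**Conclusion.** The point holds as a conflict in the recording rule. Protocol 12.1 makes attribution to natural history a condition for recording worsening, whereas 12.3 excludes causal judgement from the definition of an AE. Sites may therefore record post-procedure ear events differently, and the clause can bias the by-subject ear-AE rate only downward. This rests on the plain reading of the visible text and on the absence of a control arm. No size can be stated.

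A reader might be tempted by two stronger conclusions that the documents do not support:

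- **A size from the entry frequencies.** One could project the AOM rate required for enrolment into follow-up and call the result the number of lost events. That calculation assumes unchanged frequency. Episodes at an unchanged frequency are left out by the ordinary pre-existing-condition rule, whatever the natural-history clause says. It would also assume no benefit from the tube and cover only the recurrent-AOM children, whose share is not given.
- **Irrecoverable loss.** Patency, tympanometry, otoscopy and medication data allow part of the picture to be rebuilt, as shown above.

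**What to change.** In Protocol 12.1:

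- Delete the natural-history qualifier, so that the exception ends at worsening in severity or frequency.
- State that the following are recorded as AEs in a treated ear after the procedure: any new episode of acute otitis media or otorrhea, any recurrence or worsening of effusion, and any tube blockage. Persistent effusion unchanged from baseline need not be recorded, since that would count the enrolling disease as harm.
- State that attribution to the disease is made only through the Table 7 causality category.

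Both the deletion and the list are needed. The deletion deals with worsening. The list settles that a discrete new episode is recorded even when its frequency matches the child's history. The SAP 14.1 tables by relationship would then show total and related rates side by side.

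The change is confined to protocol wording and case report form guidance. Its price is more non-serious AE records and a higher, less favorable overall AE rate. The related-event tables are kept.

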12.2. Serious Adverse Events

If an unexpected serious complication resulting in an adverse event occurs during the procedure, the procedure will be terminated. The Investigator will take all appropriate intra- and post-procedural measures to ensure subject safety and proper treatment. In the event of a serious adverse event at any time during the study, the Investigator will notify the Sponsor and their IRB immediately or no later than within 24 hours.

All Serious Adverse Events that have not resolved by the end of the subject's participation in the study must be followed until the event resolves, improves, or stabilizes. The investigator should report any follow-up information as it becomes available.

12.3. Adverse Event Definitions

Adverse Event (AE)

An AE is any unfavorable and unintended sign, symptom, or disease temporally associated with the procedure or use of the device or investigational drug, and does not imply judgment about causality.

Serious Adverse Event (SAE)

AEs are classified as serious or non-serious. A serious adverse event is any AE that is:

- Fatal
- Life-threatening
- Requires or prolongs hospital stay

- Results in persistent or significant incapacity or substantial disruption of the ability to conduct normal life functions
- Led to fetal distress, fetal death or congenital abnormality or birth defect
- An important medical event that may jeopardize the subject, and may require medical or surgical intervention to prevent one of the other serious outcomes noted above.

Life Threatening Adverse Event or Life-Threatening Suspected Adverse Reaction

An adverse event or suspected adverse reaction is considered life threatening if, in the view of either the investigator or sponsor, its occurrence places the subject at immediate risk of death. It does not include an adverse event that, had it occurred in a more severe form, might have caused death.

Unanticipated Adverse Device Effect (UADE)

A UADE is any serious adverse effect on health or safety or any life-threatening problem or death caused by, or associated with, a device, if that effect, problem or death was not previously identified in nature, severity, or degree of incidence in the investigational plan or application, or any other unanticipated serious problem associated with a device that relates to the rights, safety, or welfare of subjects.

In order to ensure subject safety during the study, all adverse events assessed as “serious” in the opinion of the Investigator will be reviewed by the Medical Monitor to determine any causal relationship to the study drug, device or procedure. All adverse events that do not meet any of the criteria for serious should be regarded as non-serious adverse events. Non-serious adverse events must still be documented on the appropriate CRF.

Reporting

The sponsor will notify FDA, all reviewing IRBs and all participating Investigators of potential serious risks, from this study or any other source, as soon as possible, but in no case later than 15 calendar days after the Sponsor determines that the information qualifies for reporting, including:

1. Suspected adverse drug reactions that are considered both serious and unexpected,
2. Findings from other studies that suggest a significant risk in humans exposed to the drug,
3. Findings from animal or in vitro testing that suggest a significant risk in humans exposed to the drug, and
4. An increased rate of occurrence of serious suspected adverse reactions.

In addition, the sponsor will notify FDA, all reviewing IRBs and participating investigators within 10 working days after the Sponsor first receives notice of an Unanticipated Adverse Device Effect.

Health Canada Reporting

Investigational Drug AE Reporting:

The sponsor will notify Health Canada or any serious unexpected adverse drug reaction

- Where it is neither fatal nor life-threatening, within 15 days after becoming aware of the information;
- Where it is fatal or life-threatening, within 7 days after becoming aware of the information.

Investigational Device AE Reporting:

The sponsor will notify Health Canada of any incident involving the investigational device that:

- Is related to a failure of the device or a deterioration in its effectiveness, or any inadequacy in its labelling or in its the directions for use; and
- Has led to the death or a serious deterioration in the state of health of a patient, user or other person or could do so were it to recur.

Preliminary Health Canada reporting timelines:

- Within 10 days after Sponsor becomes aware of an incident, if the incident has led to the death or a serious deterioration in the state of health of a patient, user or other person, or
- Within 30 days after the Sponsor becomes aware of an incident, if the incident has not led to the death or a serious deterioration in the state of health of a patient, user or other person, but could do so were it to recur.

12.4. Adverse Event Classification

Adverse Event Severity

Ear-related adverse events will be classified as to the severity of the event based on the definitions consistent with AE severity grading scale provided by the National Cancer Institute, of the NIH and US Department of Health and Human Services – Common Terminology Criteria for Adverse Events v.4.03 (CTCAE) June 14, 2010 (**Table 5**).⁶⁶ Grade level of adverse event refers to the severity of the event. [REDACTED]

[REDACTED]

[REDACTED]

[REDACTED]

Table 5. Table of Ear-related Adverse Event Severity

Adverse Event	Grade 1	Grade 2	Grade 3	Grade 4	Grade 5
Ear pain	Mild pain	Moderate pain; limiting instrumental activities of daily living (ADL)	Severe pain; limiting self care ADL	-	-
External ear inflammation	External otitis with erythema or dry desquamation	External otitis with moist desquamation, edema, enhanced cerumen or discharge; tympanic membrane perforation; tympanostomy	External otitis with mastoiditis; stenosis or osteomyelitis; necrosis of soft tissue or bone	Urgent operative intervention indicated	Death
External ear pain	Mild pain	Moderate pain; limiting instrumental ADL	Severe pain; limiting self care ADL	-	-
Middle ear inflammation	Serous otitis	Serous otitis, medical intervention indicated	Mastoiditis; necrosis of canal soft tissue or bone	Life-threatening consequences; urgent intervention indicated	Death
Tinnitus	Mild symptoms; intervention not indicated	Moderate symptoms; limiting instrumental ADL	Severe symptoms; limiting self care ADL	-	-
Vertigo	Mild symptoms	Moderate symptoms; limiting instrumental ADL	Severe symptoms; limiting self care ADL	-	-
Vestibular disorder	-	Symptomatic; limiting instrumental ADL	Severe symptoms; limiting self care ADL	-	-
Ear - Other	Asymptomatic or mild symptoms; clinical or diagnostic observations only; intervention not indicated	Moderate; minimal, local or noninvasive intervention indicated; limiting age-appropriate instrumental ADL	Severe or medically significant but not immediately life-threatening; hospitalization or prolongation of existing hospitalization indicated; disabling; limiting self care ADL	Life-threatening consequences; urgent intervention indicated	

Table 6. Table of Other Events Adverse Event Severity

Adverse Event	Grade 1 (Mild)	Grade 2 (Moderate)	Grade 3 (Severe)	Grade 4 (Potentially Life Threatening)
Nausea/Vomiting	No interference with activity or 1-2 episodes/24 hours	Some interference with activity or >2 episodes/24 hours	Prevents daily activity, requires outpatient IV hydration	ER visit or hospitalization for hypotensive shock
Diarrhea	2-3 loose stools or <400 gms/24 hours	4-5 stools or 400-800 gms/24 hours	6 or more watery stools or >800 gms/24 hours or requires outpatient IV hydration	ER visit or hospitalization
Headache	No interference with activity	Repeated use of non-narcotic pain reliever > 24 hours or some interference with activity	Significant; any use of narcotic pain reliever or prevents daily activity	Significant; prevents daily activity
Fatigue	No interference with activity	Some interference with activity	Significant; prevents daily activity	Significant; prevents daily activity
Myalgia	No interference with activity	Some interference with activity	Significant; prevents daily activity	Significant; prevents daily activity
Illness or clinical adverse event	No interference with activity	Some interference with activity not requiring medical intervention	Prevents daily activity and requires medical intervention	Significant; prevents daily activity

Other adverse events (**Table 6**) will be classified as to the severity of the event based on the definitions consistent with AE severity grading scale provided by FDA Guidance (Sep 2007) entitled “Toxicity Grading Scale for healthy Adult and Adolescent Volunteers Enrolled in Preventive Vaccine Clinical Trials”.⁶⁷ Grade level of adverse event refers to the severity of the event.

Any increase in the severity of an AE should be documented.

Adverse Event Causality

Causality regarding device, drug and/or procedure relationship will be assigned by the Investigator to all adverse events according to the definitions provided in **Table 7**.

Table 7. Table of Adverse Event Causality

Causality	Description*
Certain	A clinical event, including laboratory test abnormality, occurring in a plausible time relationship to procedure, device or drug administration/exposure, which cannot be explained by concurrent disease, other interventions or other drugs and considered definitely related to the study drug, device or procedure.
Probable	A clinical event, including laboratory test abnormality, with a reasonable time sequence to procedure, device or drug administration/exposure, unlikely to be attributed to concurrent disease, other interventions or drugs.
Possible	A clinical event, including laboratory test abnormality, with a reasonable time sequence to procedure, device or drug administration/exposure, but which could also be explained by concurrent disease, other interventions or drugs.
Not Related	A clinical event, including laboratory test abnormality, with a temporal relationship to procedure, device or drug administration/exposure which makes a causal relationship improbable, and in which concurrent disease, other interventions, other drugs or chemicals provide plausible explanations. A Not Related event may also not have a reasonable temporal relationship to procedure, device or drug administration/exposure.

*Causality definitions derived from WHO-UMC Causality Assessment Scale⁶⁸

Adverse Event Criteria – Hearing Loss

Audiometry will be used to assess changes to hearing thresholds for all ears. Investigators will diagnose post-treatment hearing impairment/loss if audiometry indicates a greater than 15-decibel (dB) change (worsening) in air conduction pure tone average for either ear. Classification of the level of hearing loss/impairment will be according to the American Academy of Audiology Childhood Screening Guidelines, as outlined in **Table 8**.^{69,70}

Table 8. Table of Hearing Threshold Change (Worsening) Classification

Level	Threshold Change
Slight	16-25 dB
Mild	26-40 dB
Moderate	41-55 dB
Moderately Severe	56-70 dB
Severe	71-90 dB
Profound	91 dB or greater

[figure not shown]
